Genetic sample				X															Any time predose on Day 1 This research may be described in a separate ICF or as part of a combined ICF. A separate signature is required where participant participation is optional		
Study intervention				X			←=====X=====→														
Telemetry				X															Telemetry performed starting 30 (±10 min) pre-dose to 12 hr (±20 min) post-dose		
AE review					←=====X=====→																
SAE review	←=====X=====→																				
Concomitant medication review	←=====X=====→																				

Part B .2- 7 Day Repeat Dose																			
Procedure	Screening (up to 30 days before Day 1)	Intervention Period [Days] (for each dosing cohort)															E.D	Follow-up (~14±1 days post last dose)	Notes E.D = early discontinuation/withdrawal
		-2	-1	1	2	3	4	5	6	7	8	9	10	11	12	13			
Urine sampling PD			X ⁸	X ⁹						X ⁹				X ⁹			(X)	
⁸combined void for windows of 24-22 hr, 22-20 hr, 20-18 hr, 18-16 hr, 16-12 hr, and 12-0 hr predose.
 
⁹combined void for windows of 0-2 hr, 2-4 hr, 4-6 hr, 6-8 hr, 8-12 hr, and 12-24 hr post-dose
 
Aliquots will be removed prior to pooling for urine PK. Total urine volume will be recorded before aliquots for PD are removed.
	

Part B .2- 7 Day Repeat Dose																			
Procedure	Screening (up to 30 days before Day 1)	Intervention Period [Days] (for each dosing cohort)															E.D	Follow-up (~14±1 days post last dose)	Notes E.D = early discontinuation/withdrawal
		-2	-1	1	2	3	4	5	6	7	8	9	10	11	12	13			
24h urine sampling for PK and metabolite profiling			X	X											X			(X)	
Voids from urine pharmacodynamic (PD) sampling windows will be combined into 0-24 hr pools on Day -1,1, and 10 after aliquoting for PD.
 
These voids will be combined for PK/metabolite analysis only after aliquots for urine PD are removed
 
See study reference manual (SRM) for details on samples and processing

Part B .2- 7 Day Repeat Dose																					
Procedure	Screening (up to 30 days before Day 1)			Intervention Period [Days] (for each dosing cohort)													E.D	Follow-up (~14±1 days post last dose)	Notes E.D = early discontinuation/withdrawal		
				-2	-1	1	2	3	4	5	6	7	8	9	10	11				12	13
Blood sampling for PK						X ¹⁰						X ¹¹	X ¹¹			X ¹¹		X ¹⁰	(X)	¹⁰ Day 1 and Day 10: Predose, 5 min, 30 min, 1 hr, 1.5hr, 2 hr, 3 hr, 4 hr, 6 hr, 8 hr, 10 hr, 12 hr, 18 hr, 24 hr, 36 hr, 48 hr, 60 hr, and 72 hr post-dose ¹¹ pre-dose samples collected on days 6, 7, and 9	
Blood sampling for metabolite profiling						X												X		Day 1 and Day 10 Predose, 5 min, 30 min, 1 hr, 1.5 hr, 2 hr, 3 hr, 4 hr, 6 hr, 8 hr, 10 hr, 12 hr, 18 hr, 24 hr, 36 hr, 48 hr, 60 hr, and 72 hr post-dose	
Blood sampling for Pharmacodynamics and biomarkers					X ¹²	X ¹²							X ¹³					X ¹³		(X)	¹² Predose and 24 hr post-dose on Day 1 ¹³ Predose Days 7 and 10

Part B .2- 7 Day Repeat Dose																				
Procedure	Screening (up to 30 days before Day 1)			Intervention Period [Days] (for each dosing cohort)														E.D	Follow-up (~14±1 days post last dose)	Notes E.D = early discontinuation/withdrawal
		-2	-1	1	2	3	4	5	6	7	8	9	10	11	12	13				
Muscle Biopsy			X ¹⁴												X ¹⁵			(X)	
Muscle biopsies must be performed AFTER clinical safety assessments on the corresponding days
 
¹⁴Day -1 muscle biopsy to occur 1-6 hr after estimated timing of initial dose on Day 1. Time of sample collection to be recorded
 
¹⁵Day 10 muscle biopsy to occur within 1-6 hr after last dose administered
 
Time of sample collection to be recorded. Muscle biopsy can be performed at any time during pre-dose period.
	

Part B .2- 7 Day Repeat Dose																				
Procedure	Screening (up to 30 days before Day 1)	Intervention Period [Days] (for each dosing cohort)															E.D	Follow-up (~14±1 days post last dose)	Notes E.D = early discontinuation/withdrawal	
		-2	-1	1	2	3	4	5	6	7	8	9	10	11	12	13				
Discharge from Clinical Unit																	X	(X)		

- The time to start the second dose in Part B can be modified based on the estimates of half-life from Part A.
- Duration of dosing in Part B can be modified based on the estimates of half-life from Part A.
- The timing and number of planned study assessments, including safety, PK, PD/biomarker or other assessments may be altered during the course of the study based on newly available data (e.g., to obtain data closer to the time of peak plasma concentrations) to ensure appropriate monitoring.
- Any changes in the timing or addition of time points for any planned study assessments as the result of emerging pharmacokinetic/pharmacodynamic data from this study must be documented and approved by the relevant study team member and then archived in the sponsor and site study files, but will not constitute a protocol amendment. The CA and EC will be informed of any safety issues that constitute a substantial amendment and require alteration of the safety monitoring scheme or amendment of the ICF. The changes will be approved by the CA and the EC before implementation.

Part C- Food Effect									
	Screening (up to 30 days before Day 1)	Treatment Period [Days] (with or without food)					E.D.	Follow-up (~14±1 days post last dose)	Notes E.D = early discontinuation/withdrawal
		-1	1	2	3	4			
Informed consent	X								
Inclusion and exclusion criteria (including drug screens)	X		X						Recheck clinical status before randomization and/or 1st dose of study medication.
Demography	X								
Physical examination including height and weight	F	B				B	(B)	F	F: Full exam; B: Brief Exam; height is only taken once at screening

Part C- Food Effect									
	Screening (up to 30 days before Day 1)	Treatment Period [Days] (with or without food)					E.D.	Follow-up (~14±1 days post last dose)	Notes E.D = early discontinuation/withdrawal
		-1	1	2	3	4			
Medical history (includes substance usage and family history of premature CV disease and any changes in health status occurring between screening and admission to the unit)	X	X							Substances: Drugs, Alcohol, tobacco, and caffeine
Past and current medical conditions	X	X							
HIV, Hepatitis B and C screening	X								If test otherwise performed within 3 months prior to first dose of study intervention, testing at screening is not required
Admission to Clinical Unit		X							

Part C- Food Effect									
	Screening (up to 30 days before Day 1)	Treatment Period [Days] (with or without food)					E.D.	Follow-up (~14±1 days post last dose)	Notes E.D = early discontinuation/withdrawal
		-1	1	2	3	4			
Safety Laboratory assessments (including liver chemistries)	X	X	X	X	X	X	(X)	X	Predose; 8 hr, 24 hr, 48 hr, and 72 hr post-dose and at follow-up visit
Routine Urinalysis	X		X	X	X	X	(X)	X	Predose; 8 hr, 24 hr, 48 hr, and 72hr post-dose and at follow-up visit
12-lead ECG	X	X	←-----X-----→				(X)	X	ECGs assessed at screening (triplicate) and admission (single). During treatment period ECGs assessed predose (triplicate at least 5 min intervals) and single measurements postdose every 30 min for 1 hr, hourly up to 6 hr, and at 12 hr, 24 hr, 36 hr, 48 hr, and 72 hr post-dose

Part C- Food Effect									
	Screening (up to 30 days before Day 1)	Treatment Period [Days] (with or without food)					E.D.	Follow-up (~14±1 days post last dose)	Notes E.D = early discontinuation/withdrawal
		-1	1	2	3	4			
Vital signs (pulse rate, bp, respiratory rate, and oral temperature)	X	X	←-----X-----→				(X)	X	Vitals assessed at screening (triplicate measurements for pulse and bp) and admission (single measurements). During treatment period vitals assessed predose (triplicate measurements for pulse and bp) and postdose (single measurements) every 15 min for 1 hr, hourly up to 6 hr, and at 12 hr, 24 hr, 36 hr, 48 hr, and 72 hr post-dose See Section 8.2.2. in Protocol for further information
Randomization			X						

Part C- Food Effect									
	Screening (up to 30 days before Day 1)	Treatment Period [Days] (with or without food)					E.D.	Follow- up (~14±1 days post last dose)	Notes E.D = early discontinuation/withdrawal
		-1	1	2	3	4			
Genetic sample			X						Sample can be obtained at any point during dosing. This research may be described in a separate ICF or as part of a combined ICF. A separate signature is required where participant participation is optional
Test Meal			X						Fed Arm only. See Section 5.3.1. in Protocol for timings regarding meals, fasting, and treatment administration
Study intervention			X						
Telemetry			X						Telemetry performed starting 30 min (±10 min) pre-dose to 12hrs (±20 min) post-dose
AE review			←-----X-----→				(X)	X	
SAE review	X		←-----X-----→					(X)	

Part C- Food Effect									
	Screening (up to 30 days before Day 1)	Treatment Period [Days] (with or without food)					E.D.	Follow- up (~14±1 days post last dose)	Notes E.D = early discontinuation/withdrawal
		-1	1	2	3	4			
Concomitant medication review	X	←-----X-----→					(X)	X	
Blood sampling for PK			←-----X-----→					³ Pre-dose, 5 min, 30 min, 1 hr, 1.5 hr, 2 hr, 3 hr, 4 hr, 6 hr, 8 hr, 10 hr, 12 hr, 18 hr, 24 hr, 36 hr, and 48 hr, 60 hr, and 72 hr post-dose	
Discharge from Clinical Unit						X	(X)		

- Duration of dosing in Part C can be modified based on the estimates of half-life from Part A.
- The timing and number of planned study assessments, including safety, PK, PD/biomarker or other assessments may be altered during the course of the study based on newly available data (e.g., to obtain data closer to the time of peak plasma concentrations) to ensure appropriate monitoring.

Any changes in the timing or addition of time points for any planned study assessments as the result of emerging pharmacokinetic/pharmacodynamic data from this study must be documented and approved by the relevant study team member and then archived in the sponsor and site study files, but will not constitute a protocol amendment. The CA and EC will be informed of any safety issues that constitute a substantial amendment and require alteration of the safety monitoring scheme or amendment of the ICF. The changes will be approved by the CA and the EC before implementation.

13.3. Appendix 3: Assessment Windows

Nominal time will be used for all analysis except PK analysis where planned and actual time will be used.

13.4. Appendix 4: Study Phases and Treatment Emergent Adverse Events

13.4.1. Study Phases

Assessments and events will be classified according to the time of occurrence relative to study treatment

Study Phase	Definition
Pre-Treatment	Date ≤ Study Treatment Start Date
On-Treatment	Study Treatment Start Date < Date ≤ Study Treatment Stop Date + 3 days
Post-Treatment	Date > Study Treatment Stop Date + 3 days

Note: Estimated half-life of GSK3439171 is approx. 13 hours. The maximum of (5 half-lives ~ 65 hours ~ 3days) and after the Study Treatment End Date, lag time have been considered to be 3 days to define the end of treatment phase.

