13.6. Appendix 6: Derived and Transformed Data

13.6.1. General

Multiple Measurements at One Analysis Time Point

 • Mean of the measurements will be calculated and used in any derivation of summary statistics but if listed, all data will be presented. • If there are two values within a time window the value closest to the target day for that window will be used. If values are the same distance from the target, then the mean will be taken. • Participants having both High and Low values for Normal Ranges at any post-baseline visit for safety parameters will be counted in both the High and Low categories of “Any visit post-baseline” row of related summary tables. This will also be applicable to relevant Potential Clinical Importance summary tables.
Study Day and Period Study Day

In PART A and C, Period Study day is calculated as the number of days from first Dose Date in the period for each subject as follows:
 
 • Ref Date = Missing → Period Study Day = Missing • Ref Date < First Dose Date in the period → Period Study Day = Ref Date – First Dose Date in the period • Ref Date ≥ First Dose Date in the period → Period Study Day = Ref Date – First Dose Date in the period + 1 
In Part A, B & C: Study day is calculated as the number of days from First Dose Date in each Cohort for each subject as:
 
 • Ref Date = Missing → Study Day = Missing • Ref Date < First Dose Date → Study Day = Ref Date – First Dose Date • Ref Date ≥ First Dose Date → Study Day = Ref Date – (First Dose Date) + 1
Change from baseline and Percentage change from baseline definition

Change from Baseline = Post-Dose Visit Value – Baseline (For Part A & C, corresponding period baseline should be considered as baseline)
 
Percentage Change from Baseline = ((Post-Dose Visit Value – Baseline)/Baseline)*100 (For Part A & C, corresponding period baseline should be considered as baseline)
 
 • Unless otherwise specified, the baseline definitions specified in Section 5.2 Baseline Definition will be used for derivations for endpoints / parameters and indicated on summaries and listings • Unless otherwise stated, if baseline data is missing no derivation will be performed and will be set to missing
Displays

- Compound ID should be used as GSK3439171 for the displays

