13.7.2.1. Handling of Missing and Partial Dates

Element	Reporting Detail
General	
 • Partial dates will be displayed as captured in subject listing displays.
Adverse Events	
 • The Clinbase allows for the possibility of partial dates (i.e., only month and year) to be recorded for AE start and end dates; that is, the day of the month may be missing. In such a case, the following conventions will be applied for calculating the time to onset and the duration of the event: 
 ○ Missing Start Day: First of the month will be used unless this is before the start date of study treatment; in this case the study treatment start date will be used and hence the event is considered On-treatment as per Appendix 4: Study Phases ○ Missing Stop Day: Last day of the month will be used, unless this is after the stop date of study treatment; in this case the study treatment stop date will be used. • Completely missing start or end dates will remain missing, with no imputation applied. Consequently, time to onset and duration of such events will be missing.
Concomitant Medications/Medical History	
 • Partial dates for any concomitant medications recorded in the CRF will be imputed using the following convention: 
 ○ If the partial date is a start date, a '01' will be used for the day and 'Jan' will be used for the month ○ If the partial date is a stop date, a '28/29/30/31' will be used for the day

Element	Reporting Detail
	
(dependent on the month and year) and 'Dec' will be used for the month.
 
 • The recorded partial date will be displayed in listings. • For each period in crossover design: 
 ○ If start date is completely missing, then we assume the medication has been taken from the beginning of the study ○ If stop date is completely missing, then we assume the medication has been taken until the end of the study

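### The SAP's phase table makes the treatment start date Pre-Treatment while its imputation rule calls the same date On-treatment, and the cap on a missing AE stop day can put the stop before the onset

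*SAP*

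**What the plan says.** SAP 13.4.1 (Appendix 4) sets three phases. Pre-Treatment is "Date ≤ Study Treatment Start Date". On-Treatment is "Study Treatment Start Date < Date ≤ Study Treatment Stop Date + 3 days". Post-Treatment is anything later.

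SAP 13.7.2.1 deals with AEs for which only month and year were recorded. It says that "the following conventions will be applied for calculating the time to onset and the duration of the event". A missing start day becomes the first of the month. If that falls before treatment began, then "in this case the study treatment start date will be used and hence the event is considered On-treatment as per Appendix 4". A missing stop day becomes the last of the month, "unless this is after the stop date of study treatment; in this case the study treatment stop date will be used". The rule does not mention the onset date, and no floor at onset appears elsewhere in the SAP.

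Protocol 8.3.1 opens AE collection when dosing begins and closes it at follow-up, which the Schedule of Activities places about 14±1 days after the last dose. Earlier occurrences go to medical history. The exception is SAEs related to study participation or to a sponsor product, which are recorded from consent.

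**The concern.** The imputation rule cites a table for a result that the table denies, so a programmer cannot follow both. The phase table is also the only rule in the SAP that assigns AEs to a treatment phase. Under Protocol 8.3.1, apart from the SAEs recorded from consent, an AE dated on the first dosing day began after the dose. Labelling it Pre-Treatment points away from the drug on the day when first exposure occurs.

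The stop-day cap is a different fault in the same section. Collection runs about two weeks past the last dose, and On-Treatment itself runs three days past it. AEs that begin after the last dose are therefore expected, and for these the cap produces an impossible date whenever the stop day is missing.

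**Working it through.** **Inputs.** Phase rules: SAP 13.4.1. Imputation rules: SAP 13.7.2.1. Collection window: Protocol 8.3.1 and 1.3. Last dose on Day 17 in the 14-day cohorts of Part B: Protocol 1.3.

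**Assumptions.** The treatment stop date is the date of the last dose. The recorded stop month is not earlier than the onset month. AE duration is stop − onset + 1, because the SAP gives no AE-duration formula.

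**The plan's own figure.** The three-day lag in SAP 13.4.1 reproduces: 5 × 13 h = 65 h, and 65/24 = 2.7 days, rounded to 3. It is not in dispute.

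**Part 1, the boundary.** Let S be the start date, E the stop date and D the AE date. The table gives Pre if D ≤ S and On if S < D ≤ E + 3. Put D = S. Then S ≤ S is true and S < S is false, so the AE is Pre-Treatment. SAP 13.7.2.1 says On-treatment for this same value. Reading the date as a date-time does not rescue an imputed value, because one set equal to the start still meets ≤ and fails <. The same substitution applies to an AE with a fully known onset date equal to S. On the calendar dates that the table uses, it is Pre-Treatment whatever the hour.

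**Part 2, the cap.** Let O be a known onset with O > E, and M the last day of the recorded stop month. Then M ≥ O > E, so the cap always applies and the imputed stop is E, which is before O. With O = E + k, duration = E − (E + k) + 1 = 1 − k. For k from 1 to 15, which covers follow-up at 14±1 days, duration runs from 0 to −14 days.

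**Illustration with invented dates.** 14-day Part B schedule: first dose 10 May (Day 1), last dose 26 May (Day 17), On-Treatment to 29 May.

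- AE in May, start day missing: imputed onset 10 May. Table: Pre-Treatment. SAP 13.7.2.1: On-treatment.
- AE with known onset 29 May, stop day missing in May: 31 May is later than 26 May, so stop = 26 May. Duration = 26 − 29 + 1 = −2 days, although the AE is itself On-Treatment.
- AE with known onset 3 June, stop day missing in June: stop = 26 May, 8 days before onset. Duration = −8 + 1 = −7 days.
- AE with onset 24 May that ended on 30 May, stop day missing: stop = 26 May. Duration = 3 days instead of 7.
- AE in June with both days missing: onset 1 June, stop 26 May, again reversed. With both days missing in May, onset is 10 May and stop 26 May, which is in order.

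Onsets from first to last dose give no negative duration. They are only cut short, and only when the AE runs past the last dose and its stop day is missing.

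**The case against.** The strongest reply is that the boundary is a slip in an inequality sign and the intent is clear. The table is introduced by "Assessments and events will be classified according to the time of occurrence relative to study treatment", and SAP 13.7.2.1 states On-treatment outright. Intent is indeed readable, but the table as written still gives the opposite label, and correcting it is free.

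A second reply is that little is reported by phase. This stands and sets the size. Only Table 3.3, a Part B AE summary, is split by study phase. Its programming note is blank, and Protocol 9.4 uses study phase for single versus repeat dosing, so the table may not use Appendix 4 at all. No AE-duration summary is listed. Participants are also in the unit until about 72 hours after the last dose, so missing stop days are most likely for AEs between discharge and follow-up.

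Some stronger readings are tempting, and the documents do not support them:

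- A reader might infer that first-day AEs drop out of the safety results. The all-AE tables (3.1, 3.2 and 3.4) state no On-Treatment filter, Listings 41 to 43 cover all AEs, and "Partial dates will be displayed as captured in subject listing displays".
- Because the table also covers assessments, a reader might infer that Day 1 baselines are disturbed. SAP 5.2 fixes baseline independently as the latest pre-dose value, and no assessment display is split by phase.
- A reader might take the study-day formula in SAP 13.6.1 as a further contradiction because it numbers the dosing date Day 1. It assigns no phase.

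**Conclusion.** Minor, and wrong as written on both counts. The phase table and the imputation rule contradict each other for any AE imputed to the treatment start date. The table also mislabels post-dose AEs with a known onset on the first dosing day, provided its dates are read as calendar dates. The stop-day cap gives a stop before onset for every AE with a known onset after the last dose and a missing stop day. It also shortens AEs that start on treatment and outlast it when the stop day is missing. Complete stop dates are unaffected, and completely missing ones stay missing.

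Reach is confined to Appendix 4 phase flags, Table 3.3 if it uses them, and derived AE time to onset and duration. The documents give no rate of partial dates and no AE counts, so the number of AEs affected cannot be stated. The durations of 0 to −14 days rest on the assumed duration formula; the reversal of dates does not.

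**What to change.** 1. In SAP 13.4.1, for AEs, define Pre-Treatment as onset before the first dose, using date-time if recorded and otherwise a date earlier than the start date. Define On-Treatment as onset at or after the first dose up to stop date + 3 days. An AE dated on the start date with no time is then On-Treatment, in agreement with SAP 13.7.2.1.
2. In SAP 13.7.2.1, impute a missing AE stop day as the earlier of month-end and the last contact or study end date, and never before AE onset. In the illustration, with last contact on 9 June (26 May + 14 days), the stops become 31 May for the 29 May onset and 9 June for the 3 June onset.
3. State in the Table 3.3 programming note whether study phase means the Appendix 4 phases or single versus repeat dose.
4. Appendix 4 does not say whether its dates apply per period or per study in Parts A and C. If they apply per period, assign each AE to the most recent dosing period. Otherwise an AE in washout could be Post-Treatment for one period and Pre-Treatment for the next.

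The cost is SAP wording, one programming note and two derivations. No new data are needed.
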